Sacral Neuromodulation in Dual Incontinence: Ultrasound and Afferent Nerve Sensation Assessment

(SaNDI)

PRINCIPAL INVESTIGATOR:

[name], MS
[name]
[name]
[name]
[name]
[contact]

SUB-INVESTIGATORS:

[name]
[name]
[name]
[name]

[name] [name]

Northwestern University

PARTICIPATING SITES:

Northwestern University Feinberg School of Medicine
Department of Obstetrics and Gynecology
Prentice Women's Hospital
[name]
[name]

FUNDING AGENCY:

American Urogynecologic Society

Synopsis

Title	Sacral Neuromodulation in Dual Incontinence: Ultrasound and Afferent Nerve Sensation Assessment
Short Title	SaNDI
Protocol Date	July 7, 2014
Study Duration	1.5 years
Study Center(s)	Northwestern University Feinberg School of Medicine
Objectives	
 1) To quantify the effect of sacral neuromodulation (SNM) on afferent innervation using current perception thresholds (CPT) in women with dual incontinence (urgency urinary incontinence (UUI) and fecal incontinence (FI)). 2) To identify neurophysiologic predictors of successful SNM in women with dual incontinence. 3) To quantify and compare baseline urethral and anal sphincter anatomy as assessed by ultrasound in women with dual incontinence who undergo successful and unsuccessful SNM. 4) To assess the quality of sexual relationships in women with dual incontinence and their male partners and to identify specific areas of dysfunction that are common in these patients.
Number of Subjects	30
Diagnosis and Main Inclusion Criteria	
Women with responses of at least “moderate bother” to PFDI-20 items 10 ‘do you lose stool beyond your control if your stool is loose or liquid’ and 16 ‘do you experience urine leakage associated with a feeling of urgency that is a strong sensation of needing to go to the bathroom’ will be identified through routine screening in our multidisciplinary clinic.
 
Inclusion criteria: Women over the age of 18 with idiopathic dual incontinence planning to undergo placement of a sacral nerve modulator and will be included if they have at least 5 UUI episodes on a 3-day diary and 2 FI episodes on a 7-day diary.

TABLE OF CONTENTS

Synopsis.....	2
1.0. Introduction – Background and Rationale.....	4

1.0. INTRODUCTION - BACKGROUND AND RATIONALE

1.1 Introduction

One in four women reports bothersome symptoms of a pelvic floor disorder with 16% reporting urinary incontinence (UI)¹. Likewise, 1 in 5 women with UI reports fecal incontinence (FI). Women with dual incontinence (UI/FI) often have more bothersome symptoms, quality of life impact, and sexual dysfunction than those with just UI or FI. Sacral neuromodulation is the only currently available treatment with Level 1 effectiveness data for BOTH UUI and FI. Yet, the precise mechanism of action of SNM on UI and FI is unclear. Alterations in both afferent innervation and muscular function are believed to play a critical role in etiology of UI and FI as well as patient's response to various treatments. This study aims to use innovative techniques to further our understanding of the neural and muscular alterations associated with dual incontinence AND identify potential neuromuscular mechanisms to guide treatment success. We will also study the impact of dual incontinence on sexual function in women and their partners. While many investigators have attempted to describe sexual function in women with UI and FI, few have addressed the impact the disorders may have on their partner's.

1.2 Background and Significance

1.2.1 Impact of UUI/FI on Quality of Life & Sexual Function

At least 1 in 5 women reports bothersome urgency urinary incontinence (UUI) and/or fecal incontinence (FI) with even higher prevalence rates among the elderly^{1,2}. In a large, national recent cross-sectional analysis, nearly 25% of women reported bother from at least one pelvic floor disorder¹. Urgency urinary incontinence and FI each can impact women's quality of life; however, the combination of both UUI and FI often results in even more dramatic effects on a woman's quality of life³. Urinary urgency incontinence affects women's sexual function, which often improves after treatment⁴. Likewise, FI causes mental burden and emotional frustration and is also associated with decreased sexual function^{5,6}. Although many studies evaluate SNS treatment efficacy and ability to improve quality of life, few have assessed adequately assessed sexual health. The complex relationships between urinary incontinence and a woman's self image, sense of well being, sexual activity, and sexual function is well established, and one can only assume the impact of FI or dual incontinence would be even more dramatic^{7,8}. Sexual dysfunction in the context of a relationship is a shared dysfunction.

Female partners of men with erectile dysfunction demonstrate high levels of sexual dysfunction⁹. It is reasonable to suspect UUI and FI in women have an impact on the sexual function of their male partners^{9,10}.

1.2.2 Pathophysiology of UUI/FI and Mechanism of Action of SNM

The etiologies of UUI and FI are complex and likely multifactorial; however, increasing data suggests neuromuscular dysfunction, particular alterations in afferent nerves, plays a role in both. SNM has proven effective for treatment of UUI and FI^{11,12}. Electrical stimulation is thought to modulate afferent nerves and reflex pathways, which in turn influence urinary and fecal continence mechanisms. The exact mechanism of SNM for the treatment of UUI and FI remains unclear and few data exist to guide which patients will respond to therapy. Further characterization of neural function of patients who undergo successful SNM may provide insight into appropriate patient selection as well as advance our understanding of pathophysiology of incontinence and SNM treatment.

A systematic review evaluating SNM in the treatment of lower urinary tract dysfunction, concluded SNM was clinically effective (>50% improvement) in 60-90% of women with UUI¹³. Similarly, a multi-center trial demonstrated SNM success rates of 90% for women with FI (>50% reduction in FI episodes)¹¹. Fecal incontinence symptoms improved in 49% of women with dual incontinence who underwent SNM primarily for UUI¹⁴.

Although SNM successfully improves UUI and FI in some women, there are no reliable predictors of successful symptoms resolution with SNM^{15,16}. Women > 55 and/or with >3 co-morbid conditions have lower UUI cure rates following SNM¹⁵, however, clinical phenotypes of women who *will* respond to SNM are unknown. Identification of quantifiable afferent neural and sphincter muscular parameters associated with successful SNM will aid patient selection as well as further understanding of pathophysiology of UUI/FI and mechanism of action of SNM in treating these disorders. This novel approach is the first to quantify objective afferent neural function with validated clinical measures and 3-dimensional ultrasound assessments of both the urethral and anal sphincters in women with dual incontinence.

1.3 Preliminary Work

Our team has extensive expertise and experience in neurophysiologic testing of the pelvic floor in women with urinary incontinence¹⁷. We showed improvement in urethral afferent sensation using CPT in women with UUI treated with tolterodine¹⁸. Urethral afferent sensation at stimulation frequencies corresponding to A- δ and C fibers improved after treatment, suggesting anticholinergic medications modulated urethral afferent innervation.

Urethral morphology using 2-D US is different in women with detrusor overactivity

compared to controls^{19,1}. We recently demonstrated that urethral sphincter complex was easily and reproducibly quantified using 3-D US in women with UI²⁰.

1.4 Innovation

1.4.1 Sensory Nerve Testing: Urethral and Anal Sphincters

Current Perception Threshold testing is a neurophysiologic test that uses electrical stimulation in the lower urinary tract to further clinical investigation of afferent innervation in pelvic floor dysfunction^{21,22}. CPT testing reliably uses electrical stimuli at varying frequencies to activate different subpopulations of afferent nerve fibers²¹. A constant current electrical stimulator delivers sine wave stimuli at three different frequencies, which selectively depolarize different types of sensory nerves based on variations in membrane ion channel concentration. Large myelinated A- β fibers are stimulated at 2000 Hz, smaller myelinated A- δ are stimulated at 250 Hz and unmyelinated C fibers are stimulated at 5 Hz. In vivo, A- δ fibers are activated by increased tension on the bladder wall and C-fiber activation is associated with some pathologic states²³⁻²⁵. Multiple authors described CPT testing in the bladder and/or urethra of women with lower urinary tract problems²⁶⁻²⁸. The use of CPT testing in the anus will be a novel approach to evaluate the afferent nerve function of the anus. We hope that afferent nerve function assessment can be a useful predictor of those women who will positively respond to SNM for the treatment of dual incontinence. This would alter treatment algorithm for women with UUI and FI and might potentially save women from undergoing an invasive procedure that is unlikely to improve their incontinence.

1.4.2 3-Dimensional Ultrasound Imaging: Urethral and Anal Sphincters

Ultrasound imaging of the internal and external anal sphincter as well as puborectalis are part of routine clinical care in women with FI. In fact, ultrasound evidence of sphincter defect has been associated with more severe disease²⁹. Likewise, urethral morphology using 2-D ultrasound is different in women with detrusor overactivity compared to controls. The urethral longitudinal smooth muscle thickness was decreased in women with detrusor activity¹⁹ suggesting that anatomic changes in urethral sphincter may be associated with UUI.

This proposal is highly innovative in that it addresses two common theories for etiology of UUI and FI in women: neural and muscular disruption. This study will capture 3-dimensional ultrasound imaging and measure small fiber afferent innervation to both the urinary and anal sphincter muscles. We will be able to determine associations

and relationships between sphincter size/volume and afferent nerve function in both the anal and urethral sphincters, which may further our understanding of the complex etiology of these disorders and aid in predicting treatment outcomes.

2.0 OBJECTIVES

2.1. Primary Objectives:

2.1.1. To quantify the effect of sacral neuromodulation (SNM) on afferent innervation using current perception thresholds (CPT) in women with dual incontinence (urgency urinary incontinence (UUI) and fecal incontinence (FI)).

2.2. Secondary Objectives:

2.2.1. To identify neurophysiologic predictors of successful SNM in women with dual incontinence.

2.2.2. To quantify and compare baseline urethral and anal sphincter anatomy as assessed by ultrasound in women with dual incontinence who undergo successful and unsuccessful SNM.

2.2.3. Women who undergo successful SNM will have larger urethral and anal sphincter muscles.

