5.1.3. Other Examinations Performed

5.1.3.1. 3-D Endovaginal ultrasound

3-D endovaginal ultrasound will be performed using a BK 8838 12mHz, 360degrees rotational transducer (BK Medical, Herlev, Denmark). Women will come in with a comfortably full bladder. In dorsal lithotomy, the ultrasound probe will be inserted into the vagina without excessive pressure. The correct anterior-posterior orientation will be noted using the hyperechogenic aspect of the pubic bone which will be designated the 12 o'clock position, with the anal canal at the 6 o'clock position. The operator will hold the transducer still during the image acquisition that will be performed at a length of 6 cm to scan for 60 seconds. This will yield a 3-D rendered cube to measure the urethra sphincter. This technique has previously been demonstrated^{30,31}

5.1.3.2. 3-D Endoanal ultrasound

3-D Endoanal ultrasound will be performed with a BK 2052 360degrees rotational transducer (BK Medical, Herlev, Denmark). Prior to the endoanal ultrasound exam, women will undergo a digital rectal exam to estimate the orientation of the anal canal. In the dorsal lithotomy position the probe is introduced along the axis of the anal canal until the puborectalis muscle sling is visualized. The anal canal, is divided into three sonographically distinct levels: high, mid, and low. The 3-D rendered cube is obtained at the level of the high anal canal for measurement³².

5.1.3.3. Multichannel urodynamic testing:

All women will undergo standard urodynamic studies according to International Continence Society guidelines.

5.1.3.4. Current Perception Threshold Testing*:

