6.0. STATISTICAL PLAN

6.1. Statistical Analysis:

Each sensory modality threshold as determined at each of the different anatomic sites will be evaluated separately. Sensory thresholds will be compared before and after SNM placement using paired t-test. Multivariate regression models will be used to determine clinical and neurophysiologic predictors of symptom improvement. Urethral sphincter volumes and presence/absence and size of internal and external anal sphincter defects will be compared in responders and non-responders.

6.2. Sample Size Determination:

The sample size estimate was based off data from our prior work and urethral CPT in women with overactive bladder symptoms before and after treatment of tolteradine . Assuming a mean urethral CPT of 1.3 at 250 Hz prior to treatment and a mean of 0.75 after treatment with a standard deviation of 0.66 we estimate that 13 subjects are needed to show a significant difference with a 80% power at 5% significance level. Assuming a 20% dropout rate, we will recruit 15 women and their partners.

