# Cover Page for Data Security Plan

Sponsor Name	Northwestern University
NCT ID	NCT02357784
Sponsor Trial ID	STU00098840
Official Title of the study	Sacral Neuromodulation in Dual Incontinence: Ultrasound and Afferent Nerve Sensation Assessment (SaNDI)
Document Date	2-8-2023

Each sensory modality threshold as determined at each of the different anatomic sites will be evaluated separately. Sensory thresholds will be compared before and after SNM placement using paired t-test. Multivariate regression models will be used to determine clinical and neurophysiologic predictors of symptom improvement. Urethral sphincter volumes and presence/absence and size of internal and external anal sphincter defects will be compared in responders and non-responders.

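### Hypothesis 2.2.3 concerns the size of both sphincter muscles, but for the anal sphincter section 6.1 and the SAP compare only defects, so the anal half of the hypothesis has no matching analysis

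*Protocol*

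**What the plan says.** Protocol section 2.2 lists the ultrasound aim in two parts. Item 2.2.2 is broad: "To quantify and compare baseline urethral and anal sphincter anatomy as assessed by ultrasound", by whether SNM succeeded. Item 2.2.3 is a directional statement about one property, size, in two muscles: "Women who undergo successful SNM will have larger urethral and anal sphincter muscles".

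Section 6.1 gives one sentence of ultrasound analysis: "Urethral sphincter volumes and presence/absence and size of internal and external anal sphincter defects will be compared in responders and non-responders". The SAP repeats it, including the anal part: "presence/absence and size of internal and external anal sphincter defects will be compared in responders and non-responders". The only other analysis that involves treatment success is the regression: "Multivariate regression models will be used to determine clinical and neurophysiologic predictors of symptom improvement".

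On acquisition, section 5.1.3.2 divides the anal canal into three levels and then says: "The 3-D rendered cube is obtained at the level of the high anal canal for measurement". It does not name the quantity to be measured. The rationale at the end of section 1.4.2 expects to determine associations "and relationships between sphincter size/volume and afferent nerve function in both the anal and urethral sphincters".

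**The concern.** The hypothesis and the analysis use the same kind of variable for the urethra (muscle size, analysed as volume) but different kinds for the anus (muscle size against defects). Two women with intact anal sphincters, one thin and one thick, have the same value on both planned anal variables: no defect and no defect size. The comparison therefore does not see the property that 2.2.3 is about. This is more than an omitted detail. An anal variable is specified, and describing the defect comparison more fully would not turn it into a test of muscle size.

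Followed as written, the trial could report on the urethral half of 2.2.3 and would have nothing to report on the anal half. If anal muscle size were added later, the choice of muscle, level and metric could be made after the investigators know who responded. In a study this small that choice could shape the answer.

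**Working it through.** The point is textual, so the main check sets the passages side by side.

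| Source | Urethral sphincter | Anal sphincter |
|---|---|---|
| Protocol 2.2.2 (objective) | baseline anatomy | baseline anatomy |
| Protocol 2.2.3 (hypothesis) | larger muscle | larger muscle |
| Protocol 6.1 and SAP (analysis) | volume | defect present or absent; defect size |
| Match to 2.2.2 | yes | yes, in part |
| Match to 2.2.3 | yes | no |

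**Could the 6.1 sentence mean anal muscle size?** No. In the phrase that ends with the anal sphincters, the noun compared is defects, and size belongs to that noun.

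**Could the regression fill the gap?** Not as worded. It names clinical and neurophysiologic predictors; ultrasound measures are not mentioned.

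**Could section 1.4 fill it?** No. It foresees size or volume at both sites, but relates them to nerve function, not to responder status, and it is rationale rather than analysis plan.

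**Is the measurement possible?** Probably, but it is not established. Finding and sizing internal and external sphincter defects already needs images that show those muscles. The only cube described, however, is at the high anal canal, and the text does not say that both muscles can be measured there.

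**The plan's own sample size.** The only calculation, in 6.2, is for the primary paired comparison ("Assuming a mean urethral CPT of 1.3 at 250 Hz prior to treatment", 0.75 after, SD 0.66) and gives 13. Taking 0.66 as the SD of the paired differences (an assumption) and a two-sided 5% level:

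- difference = 1.3 − 0.75 = 0.55
- n = (0.66 × (1.960 + 0.842) / 0.55)² = 11.3, so 12 by the normal approximation
- power by the noncentral t: 0.788 at 13 and 0.822 at 14

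The stated 13 is reproduced closely. It does not concern the ultrasound comparison, which has no sample size of its own.

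**Precision of the added comparison.** Section 6.2 recruits 15 women. The documents do not give the split by response, so I assume responder shares from 50% to 90%. In SD units, the half-width of the 95% CI for a mean difference is t(0.975, 13) × √(1/n₁ + 1/n₂), with t = 2.160. The last column is the standardized difference that a two-sided 5% t-test detects with 80% power.

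| Responders v non-responders | √(1/n₁ + 1/n₂) | CI half-width (SD) | Detectable difference (SD) |
|---|---|---|---|
| 8 v 7 | 0.5175 | 1.12 | 1.57 |
| 9 v 6 | 0.5270 | 1.14 | 1.60 |
| 11 v 4 | 0.5839 | 1.26 | 1.77 |
| 14 v 1 | 1.0351 | 2.24 | 3.14 |

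The synopsis gives 30 subjects. That may mean 15 women plus 15 partners (15 + 15 = 30), which the documents do not say. If it meant 30 women, t(0.975, 28) = 2.048, and the half-width would run from 2.048 × √(1/15 + 1/15) = 0.75 at 15 v 15 to 2.048 × √(1/27 + 1/3) = 1.25 at 27 v 3. On either reading the result is an estimate with a wide interval. The same holds for the urethral volume comparison already planned.

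**The case against.** The strongest reply is that the working objective is 2.2.2, and 6.1 serves it. Item 2.2.3 reads as an expectation placed after 2.2.2, and the synopsis lists only the anatomy comparison. Sphincter defects are anatomy, and section 1.4.2 gives a reason for choosing them: they have been linked to more severe disease. On this view only the wording of 2.2.3 runs ahead of the analysis, and rewording it would close the gap.

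Much of this stands. The defect comparison is justified and should stay, and narrowing 2.2.3 is a valid repair where anal muscle size cannot be measured. It does not remove the mismatch, because 2.2.3 appears under the secondary objectives as a separate statement about muscle size and no analysis addresses its anal part.

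A reader might infer more than the documents support:

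- **That anal anatomy is not analysed, or that defects are the wrong measure.** They answer 2.2.2 and need not be demoted.
- **That anal muscle size will not be measured at all.** Section 5.1.3.2 leaves the measured quantity open. What is missing is a planned comparison by response.
- **That the use of defects costs a definite amount of power for 2.2.3.** Such a figure would have to treat a defect as muscle size cut into yes or no. A defect is a different quantity, defect size is compared too, and the documents give no defect prevalence and no responder split.
- **That zero defect size in women without a defect is a flaw.** It is a valid value; it simply says nothing about how large the muscle is.

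**Conclusion.** The mismatch holds, and in both documents. As written, the plan yields no result on whether women with successful SNM have larger anal sphincter muscles; that is one of the two muscles in 2.2.3. The urethral half has a matching variable, objective 2.2.2 is served for both sites, and the primary threshold analysis is untouched. It is a worthwhile correction to a secondary hypothesis, not a threat to the trial's main result.

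The conclusion rests on the wording and needs no numerical assumption. The precision figures do: they assume 15 women (or 30), a responder share of 50% to 90%, and equal SDs in the two groups. They show only that the added comparison should be presented as an estimate with its interval. Whether it can be added depends on both anal sphincters being measurable on the planned endoanal images, which the protocol does not state.

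**What to change.** In section 6.1 and in the SAP, add a baseline anal muscle size variable for 2.2.3: thickness or volume of the internal and of the external anal sphincter on the baseline endoanal ultrasound, at a stated level where both muscles are visible. State that it is read without knowledge of response. Compare it between responders and non-responders as a mean difference with 95% CI, reported alongside urethral sphincter volume. Keep the defect comparison as it is.

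Before adopting this, confirm that the cube described in section 5.1.3.2 permits the measurement. If it does not, limit 2.2.3 to the urethral sphincter and say that the anal comparison concerns defects only.

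Cost: one or two sentences in each document, a few additional readings on images already planned, and one further imprecise secondary comparison. If the cube is adequate, no new visit or procedure is needed. The second option costs only a change of wording, but gives up the anal half of the hypothesis.

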3.0. SELECTION OF SUBJECTS

3.1 INCLUSION CRITERIA

3.1.1. Subject is a female over the age of 18 years old

3.1.2. Subject is diagnosed with idiopathic dual incontinence

3.1.3. Subject is planning to undergo placement of a sacral nerve modulator

3.1.4. Subject has at least 5 UUI episodes on a 3-day diary

3.1.5. Subject has 2 FI episodes on a 7-day diary

3.1.6. Subject has given signed, informed consent prior to registration on study

3.2 EXCLUSION CRITERIA

3.2.1. Subject has a neurologic disease

3.2.2. Subject has a disease that may impair sphincter tone or sensation

3.2.3. Subject is pregnant

